### 3.4 Protocol deviations

Important protocol deviations are defined as those likely to have a meaningful impact on study conduct or on the safety or efficacy outcomes for an individual subject. The criteria for identifying protocol deviations and classifying them as important will be defined within the appropriate protocol-specific document. All potential protocol deviations will be reviewed as part of the ongoing data cleaning process and documented prior to database lock.

All deviations will be identified and classified as important or not important. Important protocol deviations will be identified and classified by the deviation types:

- Inclusion criteria deviation
- Exclusion criteria deviation
- Withdrawal criteria deviation
- Prohibited concomitant medication use
- Incorrect treatment or dose
- Treatment non-compliance
- Procedural non-compliance

The process for identifying and categorizing prohibited medications is described in [Section 6.5](#).

The impact of the COVID-19 pandemic on study procedures/conduct (eg, missed visits, remote visits, interruption of study treatment) will be documented using the information collected on a dedicated eCRF page, the details for which are included in [Section 12.6](#).

### 3.5 Mapping of assessments

Study assessments at an Early Termination (ET) visit where the visit date is within the protocol-defined visit window of a scheduled site visit will be mapped to that scheduled site visit (this does not include home visits). Visit windows will be calculated relative to the date of first dose in PA0009 (planned at the PA0009 EV), but if the dose was missed at that visit, the date of the PA0009 EV will be used instead. The following rules will also be applied:

- If there is an existing scheduled site visit in the window and the specific assessment was performed at that scheduled visit, then the relevant assessments at the ET visit will be

---

mapped to the next scheduled site visit (regardless of whether this is within the protocol-defined visit window for that site visit).

- Study assessments at an ET visit that does not fall into the protocol-defined visit window of a scheduled site visit will be assigned to the next scheduled site visit after the date of the ET visit (regardless of whether this is within the protocol-defined visit window for that site visit).
- Mapping of an assessment to a scheduled visit will occur regardless of whether the assessment was planned to be conducted at that visit (with the exception of ADAb). For ADAb however, data will only be mapped to scheduled site visits where ADAb levels are planned to be measured. Any PK samples taken at the same ET visit will be mapped to the same scheduled visit as the ADAb.
- Additional rules regarding visit windows for PK and ADAb summaries are included in [Section 9.1](#) and [Section 9.2](#).

Unscheduled assessments where the visit date is within the protocol-defined visit window of a scheduled site visit will be mapped to that scheduled site visit (this does not include home visits). Visit windows will be calculated relative to the date of first dose in PA0009, but if the dose was missed at that visit, the date of the PA0009 EV will be used instead. The following rules will also be applied:

- If there is an existing assessment with a non-missing response (from a scheduled site visit or ET visit) in the window, the assessment will be left as unscheduled.
- Unscheduled assessments which do not fall within a protocol-defined visit window based on time since first dose (or date of PA0009 EV if the first dose was missed) will be left as unscheduled.
- Unscheduled assessments obtained at specific time points (eg, vital signs) will only be mapped to a scheduled site visit for the equivalent time point. Thus, if an assessment falls within the protocol-defined visit window of a scheduled site visit but the scheduled visit does not have a corresponding time point, the measurement will be left as unscheduled (eg, if the unscheduled time point was '1 HOUR POST DOSE' this will not be mapped to a visit at which only 'PRE DOSE' time points are scheduled).
- Unscheduled PK and ADAb assessments may also be mapped to a scheduled site visit if the visit date is within the protocol-defined visit window of that visit. For ADAb this will only apply to scheduled site visits where ADAb levels are planned to be measured. For any PK samples obtained at the same unscheduled visit, these will be mapped to the same scheduled visit as the ADAb.

If there are multiple unscheduled assessments in a specific visit window, the first non-missing assessment will be mapped to the scheduled visit and used for summary statistics or frequency counts. Similarly, if there are multiple scheduled assessments performed on the same visit date, the first non-missing assessment will be used for summary statistics or frequency counts.

Assessments will be reported according to the planned Schedule of Assessments ([Table 2-1](#)) and each scheduled visit summary will include actual data and any data mapped from an ET visit to

that scheduled visit. The final visit will be labeled “Week 104”. Data obtained at scheduled visits will be reported as per the database (ie, these will not be remapped as described above).

Assessments mapped to visits at which the assessment was not planned and unscheduled assessments that are not mapped to a scheduled visit at which the assessment was planned will be listed only.

### **3.6 Analysis sets**

Three analysis sets will be defined for this study.

#### **3.6.1 Enrolled Set**

The Enrolled Set (ES) will consist of all subjects who have given informed consent for PA0009.

#### **3.6.2 Safety Set**

The Safety Set (SS) will consist of all subjects in the ES who received at least one dose of study medication in PA0009.

All safety variables will be summarized for the SS. Pharmacokinetic and immunological variables will also be summarized on the SS.

Two Sub-populations of the SS will be defined for this study: SS Sub-population 1 will consist of all subjects in the SS who took no concomitant rescue medication in PA0009, and SS Sub-population 2 will consist of all subjects in the SS who took concomitant rescue medication in PA0009, as outlined in [Section 6.5](#). Rescue medications will be identified in the study database using the flag collected in the electronic case report form (eCRF). Concomitant medications are defined in [Section 6.4](#).

Selected summaries of the primary and secondary safety variables will be repeated for both SS Sub-populations only in the event that the number of subjects receiving rescue medication is  $\geq 10\%$  of the total number of subjects in the SS.

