7.8.1 Permitted concomitant treatments (medications and therapies)

Medication changes are permitted at any time after enrollment into this extension study. Medication changes and additions are permitted with the following guidelines:

- Nonsteroidal anti-inflammatory drugs (NSAIDs), DMARDs (methotrexate, sulfasalazine, leflunomide, apremilast), and/or joint injections may be given if deemed appropriate by the Investigator as outlined below. Subjects may receive these add-on therapies while continuing to receive bimekizumab. Under no circumstances should subjects have a concomitant biologic agent while receiving bimekizumab.
 - For subjects taking NSAIDs/cyclooxygenase-2 (COX-2) inhibitors, a change can be made to a different NSAID/COX-2. Changes from an NSAID to a COX-2 inhibitor or from a COX-2 inhibitor to an NSAID are permitted up to the maximum approved or

tolerated dose, whichever is less. Only 1 NSAID/COX-2 inhibitor may be taken at a given time.

- For subjects not taking NSAID/COX-2 inhibitors, either can be initiated, up to the maximum approved or tolerated dose, whichever is lower. Only 1 NSAID/COX-2 may be taken at a given time.
- Methotrexate may be added or increased to a maximum dose of 25mg/week, or the maximum tolerated dose, whichever is lower. The route of administration may be changed from oral to sc or from sc to oral. It is strongly recommended that subjects taking MTX should also take folic acid supplementation.
- Sulfasalazine may be given up to a maximum dose of 3g/day, or the maximum tolerated dose, whichever is lower, for peripheral arthritis symptoms.
- Leflunomide may be given at a maximum dose of 20mg/day (or an average of 20mg/day if not dosed daily), or the maximum tolerated dose, whichever is lower, for peripheral arthritis symptoms. Leflunomide should not be used concomitantly with MTX.
- Apremilast may be given at a maximum dose of 30mg twice daily, or the maximum tolerated dose, whichever is lower.
- Combination DMARDs (optimally 2) are allowed except that leflunomide and MTX may not be given together.
- No other oral DMARDs are permitted during this OLE study.
- Steroid tapers for disease activity or disease-related reasons are allowed with an average daily dose of 20mg prednisone or prednisone equivalent per day for a maximum of 14 days.

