13.2 General statistical considerations

Summary statistics will consist of frequency tables for categorical variables. For continuous variables, summary statistics will consist of number of available observations, arithmetic mean, standard deviation, median, minimum, and maximum unless stated otherwise.

In general, summary statistics will be done by randomized treatment group and by treatment group at completion of PA0008 (ie, bimekizumab 160mg Q4W or bimekizumab 320mg Q4W).

Two subpopulations will be defined for this study. Subpopulation 1 will consist of all subjects who do not receive rescue therapy according to the criteria outlined in [Section 5.1.1](#).

Subpopulation 2 will consist of all subjects who receive rescue therapy according to the criteria outlined in [Section 5.1.1](#). Analyses of the primary and secondary variables will also be done on both subpopulations.

Changes from Baseline will be calculated relative to the Baseline of PA0008. Variables measured at the start of PA0009 will be referred to as PA0009 entry values.

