#### **6.4 Past, prior and concomitant medications**

Only medications that were ongoing at the end of PA0008 or were started during PA0009 will be reported.

Concomitant medications are medications taken on at least 1 day in common with the dosing period of PA0009 (as defined in [Section 3.2.2](#)). A medication is classed as concomitant if the start date is no later than the end date of study medication in PA0009 + 28 days, and the stop date is either missing or on or after the start date of study medication in PA0009. This includes medications that started prior to dosing in PA0009 and continued after.

For the purposes of the analysis, past medications are medications that started and stopped prior to dosing in PA0008. This includes past TNF therapy as used for subgroup analyses, MI modelling and Baseline characteristics and past NSAID therapy (for Baseline characteristics).

Missing or partial medication start and stop dates will be imputed as described in [Section 4.2.3](#). Imputations will be performed before calculation of relative study days and classification as concomitant.

The number and percentage of subjects taking concomitant medications will be summarized by anatomical therapeutic chemical (ATC) class, presenting Anatomical Main Group (ATC Level 1), Pharmacological Subgroup (ATC level 3), and PT in separate tables for PsA concomitant medications and other concomitant medications, by treatment group at completion of PA0008, and overall for the SS. The complete list of PsA concomitant medications is included in the protocol [Section 7.8.1](#) and includes: NSAIDs, corticosteroids, DMARDs, (MTX, sulfasalazine, leflunomide and apremilast), and joint injections.

PsA concomitant medications will be identified following the procedure outlined in [Section 6.5](#).

All medications reported in PA0009, including flags to identify concomitant, PsA and rescue medications, start and stop days relative to the start date of study medication in PA0008, and start and stop days relative to the start of study medication in PA0009, will be listed for the ES.

A glossary of all medications including the Anatomical Main Group (ATC Level 1), Pharmacological Subgroup (ATC level 3) PT and reported term will also be presented, based on the ES.

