## 6.5 Prohibited medication and rescue therapy

The following medication categories will be identified:

- Rescue medications as defined below. Subjects in the category ‘Any concomitant rescue therapy in PA0009’ will be considered SS Sub-population 2 and other subjects will be considered SS Sub-population 1. Rescue medications will be identified in the study database using the flag collected in the eCRF.
- DMARDs to identify subgroups/covariates.
- PsA medications as defined in the protocol Section 7.8.1 (this includes DMARDs).
- Prohibited medications.

Rescue medication, DMARDs, and PsA medications will be classified into subcategories for reporting purposes. These will be reviewed and confirmed by the study physician in order to ensure that the classifications are correct.

The number and percentage of subjects who receive the following categories of rescue medication will be summarized by treatment group at completion of PA0008 and overall for the SS.

- Any rescue medication in PA0009 that is classified as a concomitant medication as defined in [Section 6.4](#).
- NSAID at PA0009 EV.
- No NSAID at PA0009 EV.
  - No NSAID at PA0009 EV and initiate NSAID [but not Cox-2 inhibitors] in PA0009 (only the initiation of NSAIDs that are classified as concomitant medications as defined in [Section 6.4](#) will be included).
  - No NSAID at PA0009 EV and initiate Cox-2 inhibitors in PA0009 (only the initiation of Cox-2 inhibitors that are classified as concomitant medications as defined in [Section 6.4](#) will be included).
- Use of MTX, sulfasalazine, leflunomide, apremilast or DMARD combinations in PA0009 (with the exception of MTX and leflunomide together). Only concomitant medications will be included as defined in [Section 6.4](#). For the programming of combination medications the following rules will be applied:
  - If any combination of DMARDs is taken at least once during the study the subject will be counted in the ‘combination of DMARDs’ main category

- If LEF and MTX are taken in combination (with or without another DMARD) at least once during the study the subject will be counted in the ‘combination of LEF and MTX’ subcategory
- If LEF is taken in combination with another DMARD (not MTX) at least once during the study the subject will be counted in the ‘combination of DMARDs (except LEF and MTX together)’ subcategory

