**Table 10-2: Exposure time at risk**

Exposure Category	Start Date	End Date	Duration of Exposure
Subjects who died d	Start date for each option as above	Date of death	End date – start date + 1

BKZ=bimekizumab; LD=loading dose.

a 140 days refer to 5 half-lives of BKZ.

b Date of last clinical contact for each subject is defined as the maximum of [last visit date including SFU visit, last AE start date (including imputed AE start dates), date of study termination or completion, last date of study drug administration following rules for partial treatment end dates as per [Section 4.2.5](#)].

c In the event that the first dose in PA0009 was more than 140 days after the last dose in PA0008, the exposure time at risk for 320mg will be calculated using PA0008 end date – PA0008 start date + 140 days.

d For subjects who died, the date of death will be used to replace the end date in the calculation of exposure time at risk only if the subject died within the ‘at risk’ interval (ie, within 140 days following the last dose [not applicable for duration on BKZ 320mg]) or if the subject died before dosing in PA0009 (for time at risk on BKZ 320mg). If the subject died more than 140 days after the last dose of BKZ in PA0009 the exposure time at risk will be calculated using the ‘at risk’ interval of 140 days. Note that date of death should be equivalent to date of last clinical contact.

In the event that a subject received an incorrect (unplanned) treatment sequence the calculations for study medication duration and exposure time at risk will be adjusted accordingly following the principles outlined above and this will be documented in the relevant dataset specifications.

Three summaries of exposure will be provided: 2 for exposure in PA0009 and 1 for exposure in PA0008 and PA0009 combined:

- For the PA0009 summary, durations of exposure and times at risk will be summarized by treatment group at completion of PA0008 and overall. This summary will be repeated by SS Sub-population.
- For the PA0008 and PA0009 combined table, the duration of exposure and time at risk for ‘BKZ 160mg/BKZ 160mgLD combined’, ‘BKZ 320mg’ and ‘BKZ Total’ will be summarized. Subjects who took bimekizumab 320mg during PA0008 will contribute to all three columns. Subjects who did not take 320mg in PA0008 will contribute to the ‘BKZ 160mg/BKZ 160mgLD’ and ‘BKZ Total’ columns.

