- All TEAEs by treatment group at completion of PA0008 and overall, by SS Sub-population.
- Serious TEAEs by treatment group at completion of PA0008 and overall.
- Serious TEAEs by treatment group at completion of PA0008 and overall, by SS Sub-population.
- All TEAEs in PA0008 and PA0009 by treatment at time of AE onset (BKZ 160mg, BKZ 320mg and BKZ Total).
  - The 'BKZ 160mg' treatment column in this table will include subjects in both the BKZ 160mgLD and BKZ 160mg treatment groups.
- Serious TEAEs in PA0008 and PA0009 by treatment at time of AE onset (BKZ 160mg, BKZ 320mg and BKZ Total).
  - The 'BKZ 160mg' treatment column in this table will include subjects in both the BKZ 160mgLD and BKZ 160mg treatment groups.
- All TEAEs by timing of onset relative to ADAb status in PA0009. This will include columns for the following (regardless of PA0008 Baseline ADAb status):
  - TEAEs starting before the first ADAb positive result in PA0009 including the PA0009 EV (includes ADAb Categories 2a, 4a and 5a).
  - TEAEs starting on the same date or after the first ADAb positive result in PA0009 including the PA0009 EV (includes ADAb Categories 2a, 4a and 5a).
  - TEAEs for subjects who are ADAb negative at all time points in PA0009 including the PA0009 EV (includes ADAb Categories 1a and 3a).

The following categories of TEAE will be summarized by MedDRA SOC, HLT, and PT, by treatment group at completion of PA0008 and overall:

- TEAEs leading to study discontinuation and/or permanent withdrawal of study medication.
- TEAEs leading to permanent withdrawal of study medication.
- TEAEs with a fatal outcome.

- All TEAEs by maximum relationship.
- Serious TEAEs by maximum relationship.
- TEAEs with a fatal outcome by maximum relationship.
- All TEAEs by maximum intensity.
- Non-serious TEAEs reported by more than the reporting threshold of 5% of subjects. The cut-off will be applied before rounding on each treatment group and overall.

A further summary will be presented by treatment group at completion of PA0008 and overall displaying the frequency of TEAEs by descending frequency of PT.

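### Rescue sub-populations are set by rescue at any time in PA0009, so adverse events and time before rescue count as rescued, which mainly dilutes any true difference

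*SAP*

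**What the plan says.** **Membership.** SAP 3.6.2: "SS Sub-population 2 will consist of all subjects in the SS who took concomitant rescue medication in PA0009". SAP 6.5 completes the split: subjects with any concomitant rescue therapy in PA0009 "will be considered SS Sub-population 2 and other subjects will be considered SS Sub-population 1". Protocol 13.2 also works at subject level: "Subpopulation 2 will consist of all subjects who receive rescue therapy according to the criteria outlined in" its rescue therapy section (5.1.1).

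**Timing of rescue.** Protocol 7.8.1: "Medication changes are permitted at any time after enrollment into this extension study". Under SAP 6.4 a drug is concomitant if "the start date is no later than the end date of study medication in PA0009 + 28 days" and it had not stopped before the first PA0009 dose. On drugs already running at entry, SAP 6.4 adds: "This includes medications that started prior to dosing in PA0009 and continued after".

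**Clock.** SAP 10.1 (Table 10-2) and 10.2.2 start PA0009 time at risk at the first PA0009 dose. It ends at the earlier of last dose plus 140 days and last clinical contact.

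**Tables affected.** SAP 10.2 lists "All TEAEs by treatment group at completion of PA0008 and overall, by SS Sub-population", with EAIR and EAER, and the same for serious TEAEs. The TEAE overview (numbers and percentages, including fatal TEAEs and those leading to discontinuation) is also repeated. For exposure, SAP 10.1 says: "This summary will be repeated by SS Sub-population". SAP 3.6.2 makes the sub-population summaries conditional on at least 10% of the Safety Set receiving rescue.

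**The concern.** Membership depends on something that happens during follow-up, but the counting starts at entry. A subject first rescued at Week 80 places 80 rescue-free weeks, and every TEAE in them, in the rescue column. A subject who leaves at Week 10 because of an adverse event has little chance of being rescued and usually stays in the no-rescue column. To be counted as rescued, a subject must first have remained in the study long enough to start rescue. This is immortal-time bias.

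I found no rule in either document that uses the date of first rescue to correct this. The affected tables carry the primary safety variables and, through the overview, the secondary one. Whatever their intended purpose, two columns of exposure-adjusted rates side by side will be read as showing whether risk differs with add-on therapy, and the definition distorts that reading.

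**Working it through.** **Time base.** The plan gives no rate or ratio to reproduce here. The follow-up length ties out: 100 × 7 + 140 = 840 days = 120 weeks, the stated maximum.

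**Assumed inputs (not in the documents).**
- *p*: share due for rescue
- *m*: mean week of first rescue
- *f*: share of events that end participation and so prevent later rescue
- *r*: true ratio of the event rate after rescue to that before

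**Closed form, low event rates.** Set the pre-rescue rate to 1.
- Sub-population 2 keeps only non-terminal events from before rescue: [(1 − f)m + r(120 − m)] / 120.
- Sub-population 1 also holds the terminal events of subjects who would have been rescued: 1 + f·p·m / [(1 − p)·120].

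With p = 0.3 and m = 50, the second expression is 1 + 0.179f.

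| f | Apparent ratio, true 1.0 | Apparent ratio, true 2.0 |
|---|---|---|
| 0 | 120/120 ÷ 1 = 1.00 | 190/120 ÷ 1 = 1.58 |
| 0.25 | 107.5/120 ÷ 1.045 = 0.86 | 177.5/120 ÷ 1.045 = 1.42 |
| 0.5 | 95/120 ÷ 1.089 = 0.73 | 165/120 ÷ 1.089 = 1.26 |
| 1 | 70/120 ÷ 1.179 = 0.49 | 140/120 ÷ 1.179 = 0.99 |

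**Simulation of the SAP's EAIR (equation 23).** The settings were 6 events per 100 patient-years, rescue hazards of 0.1 and 0.2 per year (about 17% and 30% rescued), dosing to Week 100 and time at risk to Week 120.
- With f = 0.10 to 0.50, a true 1.0 shows as 0.95 to 0.74 and a true 2.0 as 1.53 to 1.26.
- With f = 1, a true 1.0 shows as 0.52-0.55 and a true 2.0 as 1.01-1.07.

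**Sensitivity to rescue timing.**
- With f = 0, a true 2.0 shows as (12 + 2 × 108)/120 = 1.90 when m = 12, and as (90 + 2 × 30)/120 = 1.25 when m = 90. A true 1.0 stays 1.0.
- With p = 0.3 and f = 0.5, a true 2.0 shows as (202.5/120) ÷ 1.045 = 1.62 when m = 25, and as (127.5/120) ÷ 1.134 = 0.94 when m = 75.
- With f = 1, p from 10% to 50% and m from 25 to 75, a true 1.0 shows as 0.23-0.77 and a true 2.0 as 0.46-1.55.

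**Common first events.** For any TEAE at an assumed 150 per 100 patient-years and mean rescue Week 50, a true doubling shows as 1.19 by EAIR and 99.4% versus 96.8% by raw incidence. Most first events precede rescue.

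**Split at first rescue.** Dividing events and person-time at the first rescue date recovered 0.99-1.01 for a true 1.0 and 1.96-2.01 for a true 2.0 in every simulated setting.

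**Precision at the trigger.** With 20 of 200 rescued, time at risk is 20 × 840/365.25 = 46 patient-years. At 5 events per 100 patient-years that gives 2.3 expected events. The exact 95% interval for 2 events is 0.5 to 15.7 per 100 patient-years.

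**The case against.** The strongest reply is that these are descriptive tables. Neither document states that they are meant to compare risk with and without add-on therapy, and SAP 4.5 plans no multiple comparisons. Describing subjects who did or did not need rescue is a legitimate, if limited, use. The primary analysis on the full Safety Set is untouched, the tables may never be produced, and at the trigger imprecision would be large in any case. This limits the weight of the point, but side-by-side rates still need a correct denominator or a warning.

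A reader might infer that these tables will hide a doubled risk or invent a protective effect. The documents do not support that as a general statement. In the simulated settings it needs events that always end participation. TEAEs leading to discontinuation and fatal TEAEs have no planned EAIR by sub-population: they appear that way only as numbers and percentages in the overview, and as an unknown share of the all-TEAE and serious-TEAE rates. The closed form shows that a doubling can also vanish if half the events end participation and rescue comes late (mean Week 75), but nothing in the documents points to that combination. Nor does counting pre-rescue events as rescued create apparent protection. That comes from pre-rescue time being credited to rescue while terminal events stay in the other column.

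Two further qualifications stand. Rescue started up to 28 days after the last dose still counts, so leaving because of an adverse event does not strictly bar later entry to Sub-population 2. Subjects whose rescue drug was already running at entry have no misclassified time; if they predominate, the bias is smaller.

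**Conclusion.** The point holds as a bias in conditional, descriptive safety tables. Its usual effect is to pull a true increase toward 1 and to push a true ratio of 1 somewhat below 1. For the planned all-TEAE and serious-TEAE rates, a true 2.0 shows as about 1.3-1.5 and a true 1.0 as about 0.74-0.95. These figures assume 6 events per 100 patient-years, 17-30% rescued, rescue spread over the treatment period and 10-50% of events ending participation. A ratio of about 1.0 for a true doubling, or about 0.5 for no effect, belongs under the same inputs to events that always end participation. All of these are scenarios and could move either way with the actual timing of rescue. The mechanism itself rests only on the SAP's definitions.

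The SAP handles comparable states differently. Section 10.2.4 calculates time at risk separately on each side of 11 March 2020, section 10.2 divides TEAEs at the first positive antibody result, and section 3.7 assigns pooled data to the dose being received. No reason is given for treating rescue otherwise.

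**What to change.** For the conditional exposure, all-TEAE and serious-TEAE tables and the TEAE overview, report TEAEs and time at risk before versus on/after the first concomitant rescue start date.

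- **Before:** all subjects not on rescue at entry, with follow-up censored at first rescue.
- **On/after:** follow-up starts at first rescue, or at the first PA0009 dose if rescue was already running. For EAIR, count the first event within this window, with time measured from its start.
- **Same-day events:** place them in the on/after column, matching the antibody table.
- **Ever/never tables:** keep the protocol-defined versions as descriptive, with a note that they do not measure risk on add-on therapy.
- **SAP 3.10:** record the change there.

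No new data are needed: SAP 6.5 already lists rescue start dates and SAP 4.2.4 imputes partial ones. Some imputed dates fall on the first PA0009 dose, so footnote how many do.

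The cost is SAP wording and a few extra conditional tables. The remaining weakness is that the on/after column means since first rescue. It would include time after a short steroid course or a single joint injection had ended, and its label should say so.
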